# **Transnasal Humidified Rapid-Insufflation Ventilatory Exchange (THRIVE) Use in Pediatric Populations**

## **Statistical Analysis Plan**

**NCT03430206**

**July 9, 2020**

After IRB approval, patients were randomized to control or THRIVE. Controls received 100% oxygen via the side port of a Parson's laryngoscope to insufflate the oropharynx at 6-10 L/min, titrated by the anesthesiologist. THRIVE received 100% oxygen via HFNC at 2L/kg/min using an Optiflow machine. Inclusion criteria were all patients from birth to 18 years old. Exclusion criteria included papillomatosis, tracheostomy, or unrepaired heart disease.

The primary aim was surgical interruptions. A priori power calculation based on 15 pilot surgeries demonstrated the frequency of interruptions in the control to be 0.93 and 0.33 in THRIVE. Assuming a Poisson regression, 80% power, and 95% confidence interval, 27 patients in each group (54 total) were needed to demonstrate a significant difference. To account for incomplete data and dropouts, an additional 20 patients (74 total) were targeted for consent. The secondary aims were to compare differences in oxygen desaturation index (ODI), desaturations below 90%, transcutaneous carbon dioxide (tCO2), and adverse events.

Demographics and postoperative diagnoses in control and THRIVE were collected. Interruptions were defined as the need to pause surgery to provide airway support, such as mask ventilation or intermittent intubation. Pulse oximetry was recorded by second in the electronic medical record. ODI was defined as a 4% decrease in saturation from a 120 second rolling mean for greater than 10 seconds. TCO2 was recorded at procedure start and end. Adverse events (nausea, vomiting, sinus pain, throat pain, epistaxis) were recorded prior to discharge.

Outcomes were calculated using negative binomial regression with case duration as an offset in the unadjusted and adjusted models, with the exception of tCO2. Models were adjusted for postoperative diagnoses. As a result of interim analysis, it was determined that analysis of the outcome measure Absolute Incidence of Oxygen Desaturation Less than 90% would not provide statistically meaningful results when comparing the two groups, and this outcome was removed from the analysis plan.

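### Does an undefined case duration in the offset, with no model named as primary, undermine the interruption analysis?

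*SAP*

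**What the plan says.** The SAP (dated July 9, 2020, one undivided text) says: "The primary aim was surgical interruptions". It defines the outcome thus: "Interruptions were defined as the need to pause surgery to provide airway support, such as mask ventilation or intermittent intubation". Its analysis paragraph says: "Outcomes were calculated using negative binomial regression with case duration as an offset in the unadjusted and adjusted models", with tCO2 the only exception, and then: "Models were adjusted for postoperative diagnoses".

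Case duration is mentioned nowhere else. The only procedural time points named are for tCO2, which "was recorded at procedure start and end". The recording of pause times is not mentioned. Neither the unadjusted nor the adjusted model is given priority.

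The sizing rests on pilot surgeries that put the "frequency of interruptions in the control to be 0.93 and 0.33 in THRIVE", with no time unit. It continues: "Assuming a Poisson regression, 80% power, and 95% confidence interval, 27 patients in each group (54 total) were needed".

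The protocol does not fill these gaps. Its hypothesis concerns desaturation below 90%, and it has no interruption outcome, no case duration and no regression model.

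**The concern.** An exposure offset assumes that the denominator is not itself produced by the events being counted. Here the event is a stoppage. If case duration is elapsed time, a case with two interruptions is longer partly because of them. The arm with more interruptions then gets the larger denominator, and the rate ratio shrinks towards 1. The sizing figures look like interruptions per surgery, so the analysed ratio (per unit time) might not be the quantity the trial was sized on.

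The second gap is separate. Two models with no named decider leave the primary result open to choice, in a document written after an interim analysis.

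At stake would be an understated effect and lost power from the first gap, and an inflated type I error from the second.

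**Working it through.** **Inputs.** From the SAP: interruption frequencies 0.93 (control) and 0.33 (THRIVE), 80% power, 95% confidence (read as two-sided 5%), 27 per arm. Assumed, because the documents give no durations: f, the length of one pause as a fraction of pause-free case time; the coefficient of variation (CV) of case length; w, THRIVE working time divided by control working time; and four diagnosis groups.

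**1. The plan's own figure.** With (1.96 + 0.842)² = 7.85 and no time term:
- Poisson likelihood ratio: 7.85 / (2[0.93 ln(0.93/0.63) + 0.33 ln(0.33/0.63)]) = 7.85 / 0.298 = 26.4, so 27 per arm as stated.
- Difference of means: 7.85 × 1.26 / 0.60² = 27.5.
- Wald on the log rate ratio: 30.0.

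The sample size is not in dispute. A per-time calculation with mean exposure of one unit gives the same n, so the arithmetic does not settle the unit.

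**2. Pauses counted in the offset, equal working time.** The ratio is (0.33/0.93) × (1 + 0.93f)/(1 + 0.33f).

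| f | 0 | 0.067 | 0.15 | 0.30 | 0.50 |
|---|---|---|---|---|---|
| ratio | 0.355 | 0.369 | 0.385 | 0.413 | 0.446 |

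If there is no true effect (0.63 in both arms), the factor is (1 + 0.63f)/(1 + 0.63f) = 1. The pauses alone cannot create a difference.

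**3. Power at 27 per arm.** Simulation with Poisson counts, lognormal case lengths, negative binomial fit, two-sided Wald test at 5%, 2,000 runs per scenario, equal working time:

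| Case lengths | f | Elapsed offset | Pauses removed |
|---|---|---|---|
| equal | 0.067 | 76.4% | 78.5% |
| equal | 0.333 | 67.0% | 78.5% |
| CV 0.5, events scale with length | 0.067 | 77.1% | 78.6% |
| CV 0.5, events scale with length | 0.333 | 67.5% | 79.1% |
| CV 0.8, events scale with length | 0.067 | 75.6% | 78.0% |
| CV 0.8, events do not scale | 0.067 | 69.6% | 71.3% |

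Across all 15 scenarios the loss from counting pauses was 1-2 points at f = 0.067, 3-5 at f = 0.15 and 9-12 at f = 0.333. A separate Poisson simulation (3,000 runs, CV 0.5) agrees: about 80%, 78%, 72%, 67% and 58% at f = 0, 0.1, 0.2, 0.3 and 0.5.

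**4. Type I error of the alternatives.** With 0.63 in both arms, rejection was 1.2-5.5% with the elapsed offset, 3.5-7.4% with pauses removed and 3.9-6.0% with no offset. The Monte Carlo standard error at 5% is √(0.05 × 0.95/2000) = 0.5 points, so 7.4% is a real excess.

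**5. Two models.** With 1,000 runs per scenario, CV 0.5 and f = 0.10, the unadjusted and adjusted models disagreed on significance in 6-8% of trials when diagnosis was unrelated to interruptions, and in 12-15% when rates differed fivefold across diagnosis groups. Under no effect, taking whichever was significant rejected in 4.2-6.6%.

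**6. Unequal working time, f = 0.10, w from 0.8 to 1.2.** If interruptions do not depend on time:
- elapsed offset [0.33/(w + 0.33f)] / [0.93/(1 + 0.93f)]: 0.466 to 0.315;
- pauses removed (0.33/w)/0.93: 0.444 to 0.296;
- per surgery: 0.355.

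If interruptions scale with time, the elapsed ratio is 0.375 and the net ratio 0.355 throughout, while the per-surgery ratio runs from 0.284 to 0.426.

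**The case for a change.** The strongest case for a change is that both gaps bear on the primary aim and cost little to close. If each pause took a third of pause-free case time, 9-12 points of power would go. If THRIVE changed working time, a per-minute ratio and a per-surgery ratio would answer different questions. Two models that can disagree in up to 15% of trials should not be left unranked in a plan written after an interim analysis.

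Some of this stands. The definitions are missing. The conservative direction in step 2 holds only with equal working time: with no true per-surgery effect and w = 1.2, the elapsed ratio is 1.063/1.263 = 0.84. But removing pauses does not cure that, since it gives 1/1.2 = 0.83. It is a feature of any rate per unit time, and a reader can interpret it as such.

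The rest is weaker:
- The large power losses need pauses of a length that nothing in the documents supports. They are computed at exactly 27 per arm, although 74 consents were targeted; that margin is for incomplete data, but any surplus would soften the loss.
- An 8-11% false-positive rate appears only if two no-offset models are added to the choice. The SAP proposes neither.
- The interim analysis enters the SAP only in the sentence beginning "As a result of interim analysis, it was determined that analysis of the outcome measure", which concerns the count of desaturations below 90%. Nothing ties it to the interruption model.
- The SAP is written in the past tense, so the analyses may already have been run. Naming a decider now could itself be post hoc, and the documents give no ground for preferring one model.

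**Conclusion.** No change follows. The plan leaves two definitions unwritten, and harm from either is not shown.

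For the offset, recorded start-to-end time is the natural reading, and interruptions per elapsed minute is a legitimate quantity. With equal working time and assumed pauses of 7-15% of pause-free time, the ratio moves from 0.355 to about 0.37-0.39, against THRIVE, at a cost of 1-5 points of power. Removing the pauses trades that for null rejection of up to 7.4%, and needs pause times that may not exist. Because one offset serves every outcome except tCO2, the same definition would also take time out of the desaturation-index denominator, and nothing says oximetry stopped during a pause. Dropping the offset is likewise a trade-off: against the pause-free offset it loses 3-9 points of power if interruptions scale with case length and gains 3-8 if they do not.

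For the models, the SAP specifies both, and picking the better of the two rejects in 4.2-6.6% under no effect, at or slightly above 5%. Showing both results lets a reader see any disagreement. An added count model or a table of durations by arm would be extra reporting, not a correction.

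The conclusion rests on short pauses and similar working time in the two arms. Longer pauses would cost more power, but would not by themselves produce a false benefit.

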Scientific Protocol

**Transnasal Humidified Rapid-Insufflation Ventilatory Exchange (THRIVE) Use in
Pediatric Populations**

Scientific Protocol

NCT03430206

January 9, 2018

1) Name of study

Transnasal Humidified Rapid-Insufflation Ventilatory Exchange (THRIVE) Use in Pediatric Populations

2) PI and other key investigators or key study personnel

[name] – PD

[name] – COPD

[name] – other personnel

[name] - other personnel

[name] - other personnel

[name] – other personnel

[name] – other personnel

[name] - other personnel

3) Specific source of institutional funding (account number)

none

4) List of sources from whom you are seeking funds (or have sought funding) for this project

none

5) Specific aims and basic hypothesis including an explicit primary hypothesis or goal

Hypothesis: The application of THRIVE at 1-2L/kg/min up to 70L/min will reduce to incidence of desaturation events (defined by SpO₂ <90%) by 75%.

Secondary aims: to verify the safety of intraoperative use of THRIVE in pediatric populations in the operating room and assess the incidence of adverse effects.

6) General background (2 page maximum including published preclinical and animal data supporting basic hypothesis, if relevant)

The introduction of high-flow nasal cannula (HFNC) as Transnasal Humidified Rapid-Insufflation Ventilatory Exchange (THRIVE) to the operating theater has been demonstrated and validated in numerous studies in both adult and pediatric patients prior to intubation.^{1,2,3} It has including those undergoing laryngeal procedures and surgeries, to augment sedation-related hypoventilation, or as a substitute for apneic oxygenation, intermittent intubation or mask ventilation, or jet ventilation.^{4,5,6} Given the previously demonstrated safety and efficacy of high-flow nasal cannula in similar populations, we intend to study its use during relevant procedures.

7) Preliminary unpublished data (1 page maximum)

At Lucile Packard Children’s Hospital in 2017, a retrospective analysis of 3 months of eligible cases (pediatric patients undergoing microdirect laryngoscopy and bronchoscopy (MDLB) with or without other airway interventions in pediatric patients undergoing general anesthesia with a

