natural airway) was performed and demonstrated that 54.5% (24/44) experienced at least one desaturation value below 90%, and 29.5% (13/44) experienced at least one desaturation below 80%. Given the incidence of desaturation events of 54.5% and serious desaturation events of 29.5%, it is clear that the current methods utilized to oxygenate patients undergoing these procedures may have the potential for improvement.

8) Experimental design and data analysis, including inclusion and exclusion criteria, statistical basis for the number of subjects to be enrolled, the statistical plan for analyzing at least the primary hypothesis, matrix showing procedure plan for each study visit, data safety monitoring plan (4 pages maximum)

We aim to enroll approximately 40 pediatric patients scheduled to undergo otolaryngologic or endoscopic surgeries or procedures under general anesthesia. At the time of enrollment, patients will be randomized to control or intervention arms using a random number generator.

The incidence of desaturation events <90% during microdirect laryngoscopy procedures under general anesthesia at our institution over the previous 3 months has been reviewed and found to be 54.5% of cases. Given an estimated reduction in desaturation events by approximately 75%, we will plan to enroll a total of 40 patients (20 in each arm) for a power of 80%.

Inclusion criteria: Pediatric patients <18yo undergoing general anesthesia for procedures or surgeries at Lucile Packard Children's Hospital.

Exclusion criteria: Pregnancy, absence of parent or legal guardian able to provide written consent for study participation, anatomical or surgical contraindications (epistaxis, basilar skull fractures or abnormalities, nasal surgery or obstruction, nasal fractures, nasal vascular abnormalities), congenital heart disease with admixture physiology, baseline oxygen saturation < 94%, emergent surgery for which application of HFNC might delay surgery or might result in increased aspiration risk.

9) Significance (1 paragraph or less)

With this study we hope to determine whether THRIVE is superior to current oxygenation and ventilation techniques utilized during general anesthesia without an advanced airway device, and determine whether the use of THRIVE can prevent adverse events such as oxygen desaturation and its sequelae. We also hope to verify the safety of the use of HFNC during general anesthesia in pediatric patients.

10) Key references

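### The SAP drops SpO2 below 90%, the protocol's only efficacy hypothesis and sizing outcome, after an interim analysis that neither document describes

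*SAP*

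**What the plan says.** **Protocol.** Section 5 states the hypothesis that THRIVE "will reduce to incidence of desaturation events", with an event being SpO2 under 90% and a target reduction of 75%. The secondary aims there concern safety and adverse effects only. Section 7 supplies the control rate: "54.5% (24/44) experienced at least one desaturation value below 90"%. Section 8 combines that rate with the 75% reduction: "we will plan to enroll a total of 40 patients (20 in each arm) for a power of 80"%. The protocol names no statistical test and plans no interim analysis.

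**SAP.** The second paragraph makes surgical interruptions the primary aim, re-sizes on that outcome (27 per group, 74 to be consented), and moves the protocol's outcome down the list: "The secondary aims were to compare differences in oxygen desaturation index (ODI), desaturations below 90"%, then transcutaneous CO2 and adverse events. The last paragraph begins its closing sentence "As a result of interim analysis, it was determined that analysis of the outcome measure Absolute Incidence of Oxygen Desaturation Less than 90"% and ends it by saying that such an analysis "would not provide statistically meaningful results when comparing the two groups, and this outcome was removed from the analysis plan". This is the only mention of an interim analysis in either document. The third paragraph confirms that the data exist: "Pulse oximetry was recorded by second in the electronic medical record".

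**The concern.** The stated ground for removal has two features that should not occur together. It came from accruing trial data, and it concerns what the comparison between arms was expected to show. An outcome dropped on that ground is selectively reported, whether the trigger was a small difference, a low event rate or sparse data. The documents do not say which it was.

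The outcome is also not a peripheral one. It is the question the protocol posed and sized the trial to answer, and a null or imprecise result would still answer it. Without that result, and without an account of the interim look, a reader cannot judge whether the outcomes that remain were kept because of what had been seen. The SAP gives no date or reason for the change of primary outcome and does not link it to the interim look, so that sequence cannot be reconstructed either.

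**Working it through.** **1. Is SpO2 below 90% the protocol's sizing outcome?** Inputs: p1 = 24/44 = 0.545 (protocol section 7); 75% reduction (sections 5 and 8), so p2 = 0.25 × 0.545 = 0.136; power 80%; 1:1 allocation. The protocol states no alpha; I assume two-sided 0.05.

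n per arm = [1.960·√(2·p̄(1−p̄)) + 0.842·√(p1(1−p1) + p2(1−p2))]² / (p1−p2)², with p̄ = (0.545 + 0.136)/2 = 0.341.

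- First term: 1.960·√(2 × 0.341 × 0.659) = 1.314
- Second term: 0.842·√(0.248 + 0.118) = 0.509
- n = (1.314 + 0.509)² / 0.409² = 3.323 / 0.1674 = 19.9, so 20 per arm

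This matches the protocol exactly.

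**2. Does the SAP's size make the comparison uninformative?** I computed exact power by summing two binomial distributions over all tables significant at two-sided 0.05. The SAP needs 27 per arm. 37 per arm (74/2) is an upper bound, since it assumes that everyone consented is analysable and evenly split. Cells show Pearson / Fisher power.

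| Control rate | Reduction | 27 per arm | 37 per arm |
|---|---|---|---|
| 54.5% (protocol) | 75% | 92% / 86% | 97% / 96% |
| 40% | 75% | 77% / 63% | 88% / 82% |
| 30% | 75% | 61% / 42% | 73% / 63% |
| 20% | 75% | 42% / 19% | 54% / 36% |
| 54.5% | 50% | 52% / 42% | 66% / 58% |

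The 40% row is the lower 95% Wilson limit for 24/44 (0.401 to 0.683). The 30% and 20% rates and the 50% reduction are assumptions made to show the range. On the protocol's own assumptions the enlarged trial is better powered for this outcome than the protocol required. Something other than planned size lies behind the removal, and a low event rate or a smaller effect would each be enough.

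**3. What would a reported estimate look like?** The expected half-width of the 95% Newcombe interval for the risk difference, keeping the 75% reduction, is about 22 points (27 per arm) or 19 points (37 per arm) at a 54.5% control rate. At a 20% control rate it is about 18 or 16 points.

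For illustration, take counts close to the protocol's rates at 27 per arm (27 × 0.545 = 14.7; 27 × 0.136 = 3.7), that is 15/27 against 4/27:

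- Wilson limits: 0.373 to 0.724 and 0.059 to 0.325
- Risk difference: 0.556 − 0.148 = 0.407
- Lower limit: 0.407 − √[(0.556 − 0.373)² + (0.325 − 0.148)²] = 0.153
- Upper limit: 0.407 + √[(0.724 − 0.556)² + (0.148 − 0.059)²] = 0.598
- Risk ratio: 4/15 = 0.267; SE of its log = √(1/4 − 1/27 + 1/15 − 1/27) = 0.493; 95% CI 0.10 to 0.70

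These counts are hypothetical and show the protocol's hoped-for effect, not a forecast.

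**4. Does ODI stand in for the dropped outcome?** No. The SAP defines ODI by a 4% fall from a 120-second rolling mean lasting over 10 seconds. A child drifting from 92% to 89% crosses the 90% threshold with a fall of 3 points and no ODI event. A sustained fall from 100% to 95% is an ODI event that never approaches 90%.

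**The case against.** **The SAP may not remove everything.** Desaturation below 90% is still among the secondary aims, and the model sentence applies negative binomial regression with a case-duration offset to every outcome but transcutaneous CO2. What is removed is named more narrowly, as the absolute incidence. A duration-adjusted count could therefore be meant to survive. This shows that the SAP conflicts with itself and must be reconciled. It does not rescue the hypothesis: the protocol's 24/44 is an incidence, and incidence is what was removed.

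**The outcome was already secondary.** True. The SAP in force is sized on interruptions, and it calls that calculation a priori, based on 15 pilot surgeries. That is the only timing information given, and it favours the trial. The claim about sizing applies to the 2018 protocol. It remains the case that no other efficacy hypothesis stands in that protocol.

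**The removal was disclosed, and the look may have been pooled.** Disclosure is to the sponsor's credit, and a decision taken on a low pooled event rate would carry much less bias than one taken on an observed null difference. The SAP's wording about comparing the groups suggests that data by arm were seen, but that is an inference. Either way the hypothesis goes unreported.

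**The power figures do not carry the argument.** Agreed. They show only that planned size is not a sufficient explanation. The case rests on removing a hypothesis outcome for its expected between-group result.

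**Conclusion.** The concern holds, with high confidence, and the removal should be reversed before results are reported. The protocol's sole efficacy hypothesis is left without a planned analysis of the incidence it names, on a ground drawn from accruing data, at an interim look with no stated timing, number, rule or access to data by arm. The conclusion rests on the text of the two documents. The supporting figures assume a binary outcome of at least one value below 90% and two-sided alpha of 0.05. What prompted the removal, and whether arms were compared, cannot be established from the documents, and no finding is made on either.

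**What to change.** 1. Restore the outcome. For all randomised patients who had the procedure, by assigned arm, report the proportion with at least one SpO2 value below 90%, the definition behind the protocol's control rate. Give the risk difference and risk ratio with 95% CIs whatever the p-value, and the number without usable oximetry in each arm.
2. Label it as the outcome of the protocol's primary hypothesis and label surgical interruptions as the amended primary. No co-primary alpha split is needed.
3. Reconcile the secondary-aims list with the closing sentence of the SAP.
4. Keep the sentence recording the interim decision and expand it: date of the look, number of patients, event counts, who saw data by arm, any rule applied, and when and why the primary outcome was changed.

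The cost is one further analysis of oximetry already recorded each second, and a few lines of text. No patients are added, and the alpha and power for interruptions are unaffected. The drawback for the sponsor is that a possibly null or imprecise result on the protocol's hypothesis will be visible.
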